10.2 Study Assessments

Procedure	Baseline assessment (-31 days to "Day of surgery")	Pre-operative blood samples (-96 hours to "Day of surgery")	Day of surgery	Postoperative days 1, 3 and 5	30 days (can be completed retrospectively)	3 months (+- 2 weeks) and 6 months (+- 6 weeks)	12 months (+- 6 weeks)
Check eligibility criteria (by a delegated member of the research team)	х						
Informed consent	Х	х	Х				
Start CRF, record in notes, inform GP	х						
Anorectal manometry (optional)	х						Х
QOL and functional questionnaires	х					х	Х
Blood samples		х		Х			
Patient records (including adverse events)					Х	Х	X

Baseline assessments

The baseline information will be collected on the CRF (case report form) following informed consent. They will be completed by the research nurse or appropriate GCP licensed member of the surgical team. Data will include:

- (i) Socio-demographic variables: age (years), gender
- (ii) Physical examination: weight, height, BMI
- (iii) Medical history: ASA (American Society of Anaesthesiologists physical classification), previous abdominal surgery, other co-morbidities
- (iv) Radiological findings/conclusion MDT: TNM classification, mean distance from anal verge (cm)
- (v) Anorectal manometry measurement (optional)
- (vi) Patient-reported outcome measures (PROMS):Validated QOL questionnaires: EORTC-QLQ-C30 (cancer patients), C29 (colorectal cancer specific) and EQ-5D.
 - Validated functional outcome questionnaires on bowel, urological and sexual function: LARS, Vaizey score, IPSS (males), IIEF (males), FSFI (females), Kings Health (KHQ) questionnaires, see below.
- (vii) Baseline and post-operative blood samples (taken within 4 days before surgery):
 - White cell count (WCC)
 - CRP
 - Neutrophil lymphocyte ratio (NLR)
 - IL-10
 - IL-6
 - TNFa
 - MPO (neutrophil myeloperoxidase)

Questionnaire surveys will include:

- European Quality of Life-5 Dimensions (EQ-5D) this is one of the most well-known and commonly used generic measure of health status internationally, available in 169 languages and recommended by the National Institute for Health and Care Excellence (NICE) for use in its health technology appraisal process.
- European Organization for Research and Treatment of Cancer Quality of Life
 Questionnaire, EORTC QLQ-C30 and CR29 (version 3). These are cancer-specific
 and colorectal cancer-specific respectively, quality of life questionnaires that have
 been internationally validated and frequently used in the current literature.
- Low Anterior Resection Syndrome, LARS this is a simple 5-question tool established in Denmark in 2012 and validated in English in 2014. This internationally validated score attempts to specifically assess function in patients undergoing low anterior resection surgery. If patients still have a stoma in situ at 3 and/or 6 months, this questionnaire will be skipped for those timepoints.
- St Marks Faecal Incontinence tool, **Vaizey score** this questionnaire was created in 1998 at St Marks hospital in the UK and allows comparison with historical data that also used the similar Wexner score and other center's published results.
- International Prostate Symptom Score, IPSS this is a simple 8-question tool that has been validated internationally and adopted as the global standard for urological

symptom scoring. **Kings Health questionnaire, KHQ,** is a 21-item questionnaire to evaluate the impact of urinary incontinence on the quality of life in women.

Sexual function questionnaires: including International Index of Erectile Function, IIEF, for males – this is a 15-question validated questionnaire which is the most widely used to assess erectile dysfunction and considered as 'gold standard' by global health entities. The Female Sexual Functional Index (FSFI) evaluates, as the name says, the sexual function in women in 19 questions.

Questionnaire completion

If patients are included in multiple studies using one or more of the same questionnaires as described above, the research team is allowed to use these answers for this study as well, rather than burdening the patient with extra unnecessary paperwork. The criteria for this are:

- The version of the forms used for the other study is the same as the version described in this study;
- The questionnaire was completed within the appropriate timeframe as described above:
- An appropriately delegated member of the research team is responsible for trans scripting the filled in form for use in this study.

If patients are for any reason unable to complete one or more of the questionnaires, these will be noted as "unknown", and the patient will remain included in the survey. Patients will have the option for retrospective completion of the baseline questionnaires with a maximum of 30 days after the previously described timeframes.

Delays in surgery

If surgery is delayed, patients will be given the opportunity to remain in the study and consent will be reaffirmed once they have a new surgery date. If the delay is greater than 6 weeks, baseline analyses will be repeated.

Post-operative hospital admission to discharge

Patients will receive standard post-operative care as per clinical pathways, with all treatment decisions made as per clinician expertise. Study blood samples will be collected on days 1, 3 and 5. Routinely patients are expected to be discharged on day 5, but if a patient is discharged home earlier than this there will be no need for additional blood sampling after discharged. For the purpose of calibration, we may need to draw extra blood for the first 10 patients. All study bloods are to be processed as per lab manual and routine blood tests (WBC, CRP, NRL, etc.) will be processed as per local procedure.

Follow-up visits

30 days

Around 30 days postoperatively, the patient's records will be checked to assess postoperative complications, readmissions, patient related outcomes, surgical outcomes, and adverse events.

3 months

At months postoperatively, the patient will receive the questionnaire surveys to fill out (digitally or by mail) and will be contacted by the research team (digitally or by phone) for follow-up and to answer any questions regarding the study.

6 months

At 6 months postoperatively, the patient will receive the questionnaire surveys to fill out (digitally or by mail) and will be contacted by the research team (digitally or by phone) for follow-up and to answer any questions regarding the study.

12 months

At 12 months postoperatively, the patient will attend a standard care follow-up visit with the

clinical team, who will perform an anorectal manometry if possible. They will receive the questionnaire surveys to fill out (digitally, by mail or in person) and will be contacted by the research team (digitally, by phone or in person) for follow-up and to answer any questions regarding the study.

The study does not require any additional investigation or patient contact throughout its duration.

10.3 Discontinuation/Withdrawal of Patients from Study Treatment

Patients can withdraw at any point in the study without penalty. If patients withdraw any data already collected will be used and we will continue to collect outcomes from patient's medical, hospital and NHS notes, unless the patient asks us not to do so.

10.4 Definition of End of Study

The end of study will be the date of the last questionnaire assessment of the last patient.

11. ASSESSMENT OF SAFETY

11.1 Definitions

The safety of robotic and laparoscopic rectal surgery has already been established. 37–39 Robotic and laparoscopic rectal surgery is routinely practised in the participating unit. Patients are offered either surgical modality depending on surgeon and theatre availability. This study does not introduce any new therapies or treatments and does not alter post-operative care or follow up in any way. Therefore, patients are not exposed to any additional risks or complications as a result of this study. Any complications or adverse events following surgery will be highlighted and dealt with according to each unit's standard practice. Since this study does not affect the patient's normal care in any way the normal care pathways will not be altered. Therefore, there are no adverse reactions or serious adverse reactions associated with this study. Since adverse events will be dealt with according to the normal care pathways they do not need to be reported to the sponsor or the principal investigator.

Serious adverse events (SAE) are defined as adverse events that results in patient hospitalisation, a life-threatening situation or death. SAEs need to be reported in order to prevent inappropriately contacting the patient or their family to attend follow up appointments. SAEs will be identified by the research team of each unit and reported to the principal investigator.

11.2 Reporting Procedures for Serious Adverse Events

Only SAE's deemed by the PI to be directly caused by this study will be reported as SAE's. SAE's will be reported as per GCP guidelines.

11.3 Recording and Reporting Procedures for All Adverse Events

Only adverse events that are deemed by the PI to be directly caused by this study will be collected as per GCP guidelines. Venepuncture will be conducted as part of this study, and it will be conducted as per local policy. It will be done by appropriately trained and experienced staff, and will be of no greater risk than in routine clinical care.

Other adverse events will be dealt by the local hospital according to the local care pathways and do not require reporting.

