7.2 Primary and Secondary Endpoints/Outcome Measures

Primary endpoints:

- 1. Assessment of functional outcomes by using validated questionnaires for bladder, bowel and sexual function pre-operatively, and after 3, 6 and 12 months.
 - International Prostatic Symptoms Score (IPSS) (male)
 - International Index of Erectile Function (IIEF) (male)
 - Female Sexual Function Index (FSFI) (female)
 - Kings Health questionnaire (female)
 - LARS-score (male/female) Not applicable at 3 and/or 6 months if the patient still has a stoma in situ at those respective follow-up moments
 - Vaizey score (male/female)
- 2. Measurement of stress response by taking blood samples at baseline and postoperative days 1, 3 and 5. Blood samples can be collected by anyone trained to do so and will be processed by an appropriately delegated member of the clinical team (including the research team). The following blood tests will be collected:
- White blood cell count (WBC)
- C-reactive protein (CRP)
- NLR (neutrophil lymphocyte ratio)
- IL-6
- IL-10
- TNFa
- MPO (neutrophil myeloperoxidase)

Some of the above blood tests (WBC, CRP, NLR, etc.) may be carried out as part of routine post-operative care. If these results are available, they can be used and additional sampling may not be required. Should these test results also be available for postoperative days 2 and 4, they can also be collected for use in this study, but this will be optional and no additional sampling will be done on these days.

Secondary outcomes:

- 1. Quality of life assessment using validated questionnaires (EORTC QLQ-C30/ CR29 and EQ-5D) at baseline, and after 3, 6 and 12 months.
- 2. Surgical outcomes, such as operative time, blood loss, stoma application, conversion, and intra-operative complications
- 3. Patient related outcomes:
 - a. Length of hospital stay
 - b. Opioid requirements and compliance with ERP
 - c. Worst vital signs post op
 - d. Worst pain scores
 - e. Time to flatus (in days) and return of bowel function
 - f. Early morbidity (up to 30-day postoperative complications, Clavien-Dindo Classification*)
 - g. Early mortality
 - h. Adverse events.
- 4. Optional: assessment of anorectal physiology after laparoscopic or robotic surgery in rectal cancer patients by using an anorectal manometry at baseline and after 1 year

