11.4 Recording and Reporting Procedures for Complications or Death

Serious complications (leading to hospitalisation or death) need to be reported by the local research team to the principal investigator. This will be done by email or telephone and is done to ensure that the patient or their family are not inappropriately contacted to attend the follow up clinic.

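### Section 11.3 collects only study-caused adverse events, which contradicts the unrestricted adverse-event outcome in 7.2 and the records reviews in 10.2

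*Protocol*

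**What the plan says.** **Adverse events as an outcome.** The synopsis and section 7.2 (secondary outcome 3, item h) list adverse events among the patient-related outcomes. Neither limits them to events with a particular cause. Two neighbouring items in 7.2 are separate: item f, "Early morbidity (up to 30-day postoperative complications, Clavien-Dindo Classification", and item g, early mortality.

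**How they are obtained.** The schedule in section 10.2 has a patient-records row that expressly covers adverse events, marked at 30 days, at 3 and 6 months, and at 12 months. The text on the 30-day visit says the patient's "records will be checked to assess postoperative complications, readmissions, patient related outcomes, surgical outcomes, and adverse events". Again no causality limit is given.

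**What section 11 says.**
- 11.1: the study adds no treatment and no risk, and has no adverse reactions associated with it. Adverse events follow normal care, so "they do not need to be reported to the sponsor or the principal investigator". Serious adverse events, by contrast, are identified by the research team and passed to the principal investigator (PI).
- 11.2: only serious events "deemed by the PI to be directly caused by this study will be reported as" SAEs.
- 11.3: "Only adverse events that are deemed by the PI to be directly caused by this study will be collected", with a reference to GCP guidelines closing the sentence. It then adds: "Other adverse events will be dealt by the local hospital according to the local care pathways and do not require reporting".
- 11.4: "Serious complications (leading to hospitalisation or death) need to be reported by the local research team to the principal investigator".

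**The concern.** Section 11.3 uses one sentence for two different jobs. One is to decide which events enter the safety-reporting stream. In an observational study of routine surgery, it is reasonable to confine that to events caused by study procedures. The other is to decide which events are recorded as outcome data for comparing the two operations. For that purpose, whether the study caused the event is irrelevant, because the events of interest are those that follow surgery.

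As worded, 11.3 applies the first criterion to the second job. A data collector who follows it would leave surgical adverse events off the adverse-event record. One who follows 10.2 would enter them. If different staff follow different sections, the outcome is incomplete in a way that cannot be reconstructed from the dataset.

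**Working it through.** No arithmetic applies beyond counting, and the plan gives no figure to reproduce. The check sets the sections side by side.

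| Question | Synopsis, 7.2 and 10.2 | 11.3 |
|---|---|---|
| Which adverse events? | All; no limit stated | Only those the PI judges to be caused by the study |
| Source | Patient records | Not stated; depends on a PI judgement |
| When? | 30 days, 3, 6 and 12 months | Not stated |

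**Step 1: what 11.3 admits.** By 11.1, the study changes no care, adds no risk and has no associated adverse reactions. The only study procedure that 11.3 names is venepuncture, and it describes the risk as no higher than in routine care. On the protocol's own premises, the set of collectable events is therefore empty or holds a few venepuncture events.

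**Step 2: what that does to item h.** Venepuncture events do not depend on whether the operation was robotic or laparoscopic. An outcome made up of them, or of nothing, cannot show a difference between the groups.

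**Step 3: whether 11.3 can be operated.** It needs the PI to judge causality for each event, yet 11.1 says adverse events need not reach the PI. No route is given by which non-serious events would come forward to be judged.

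**Step 4: what is not lost.** Section 7.2 lists eight patient-related outcomes (items a to h), and 11.3 touches item h only. Item f covers 30-day complications by Clavien-Dindo grade. As the protocol defines the scale, grade I already takes in any departure from the normal post-operative course, so within 30 days item f captures most of what item h would. Item g covers early mortality. Readmissions are named separately from adverse events in the 30-day check. None of these carries a causality filter.

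**Step 5: where the loss falls.** What item h adds beyond items f and g is mainly adverse events after 30 days. Three of the four scheduled review points (3, 6 and 12 months) lie in that period, which is about 12 − 1 = 11 months of the 12-month follow-up.

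**Step 6: serious events.** Sections 11.1 and 11.4 send serious events to the PI whatever their cause. Section 11.2 limits what is reported as an SAE to study-caused events. These are compatible if notification to the PI and formal SAE reporting are different acts, but the protocol does not say that they are.

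**The case against.** The best defence is that 11.3 belongs to the safety chapter, refers to GCP guidelines and closes by speaking of reporting. On that reading it decides only what enters the safety stream, while 10.2 governs outcome data and already schedules the reviews without restriction. This may well be what was intended. It does not settle the matter. The verb in 11.3 is one of collection, the section heading covers recording as well as reporting and refers to all adverse events, and no exception is made for outcome data. If the defence is right, the rewording merely states it.

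Three stronger readings are tempting, and the documents do not support them.

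- *Surgical complications would go uncounted.* A reader might infer this from 11.3 alone. But 30-day complications are a separate outcome (item f), the 30-day check names them apart from adverse events, and 11.4 treats serious complications under its own heading with no causality filter. They would still be compared between groups.
- *Deaths and readmissions might not reach the team, so families could be contacted inappropriately.* This follows only if 11.2 overrides 11.1 and 11.4. Both of those require notification to the PI regardless of cause, and both give avoidance of such contact as the reason. Nothing in 11.2 withdraws that duty.
- *An unblinded PI judgement stands in front of the complication endpoints.* The judgement in 11.3 is whether the study caused the event, not whether one surgical method did, and it does not apply to items f or g or to the readmission check.

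**Conclusion.** The contradiction is real and stands in the current text; it is not a detail that a statistical analysis plan would supply. Followed literally, 11.3 leaves the adverse-event outcome (7.2, item 3h) with essentially no events and nothing to contribute to the robotic versus laparoscopic comparison.

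The size is modest. One secondary outcome and the adverse-event part of the four scheduled reviews are affected, chiefly for events after 30 days. No primary endpoint is touched. The number of events at stake cannot be given, because the protocol states no rate for adverse events beyond 30 days.

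The conclusion rests on two things: reading the collection wording in 11.3 as it stands, and accepting the statement in 11.1 that the study has no associated adverse reactions.

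**What to change.** 1. Reword 11.3 to separate recording from reporting. All post-operative adverse events found at the scheduled records reviews (30 days, 3, 6 and 12 months) are entered on the CRF as outcome data for every patient, irrespective of causality. The limit to study-caused events applies only to onward safety reporting under GCP.
2. Align 11.1, 11.2 and 11.4 with one statement: all serious events are notified to the PI, and only those judged to be caused by the study are formally reported as SAEs.
3. In 11.1, make clear that the exemption from reporting to the sponsor or PI does not exempt events from being recorded as outcomes.

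The cost is protocol wording. The records reviews are already scheduled, so no visit, sample or procedure is added. The CRF is not shown; if it lacks a field for adverse events at each review, one is needed.

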11.4 Recording and Reporting Procedures for Complications or Death

Serious complications (leading to hospitalisation or death) need to be reported by the local research team to the principal investigator. This will be done by email or telephone and is done to ensure that the patient or their family are not inappropriately contacted to attend the follow up clinic.

12. DATA HANDLING AND RECORD KEEPING

12.1 Data Collection Forms

Eligibility criteria for screening will be recorded on the screening log and if a patient is recruited, the data will initially be collected in an eCRF stored in a secure database.

Data will be collected on printed forms or digital forms and uploaded to a secure electronic database. To improve return rate of the questionnaires, patients will have the option to fill them in through a secure online survey program.

Source data/documents (such as patient notes) are kept within the participating hospital medical records department and can be accessed as required through the standard request mechanism for audit. (e)CRF's will be stored for 15 years after the study has been completed.

12.2 Data Management

All identifiable information will be held in a secure database in line with the NHS digital policy. Patient data will be pseudonymised by allocation to an individual study number. Data will be stored in a password encrypted electronic database on an NHS computer. Only the members of the direct clinical and research team will have access to patient identifiable data. Data proformas will be stored along with the consent forms and other project documents in a master file and locked in a secure office. The research fellow(s) (or appointed research nurse) will be responsible for data collection, recording and quality.

This study is compliant with the principles of the General Data Protection Regulation (GDPR, 2016) requirements.

13. DATA ANALYSIS

13.1 Description of Analysis of Populations

Subjects from each cohort will be analysed separately. The populations will be defined as per protocol analysis, e.g., patients who completed the treatment as was originally allocated will be included in the analysis, as well as eligible subjects with no minor or major protocol deviations. Descriptive statistics will be provided for all discrete variables in the form of rates and proportions with 95% confidence intervals. Continuous variables will be described by mean, standard deviation, median and range.

13.2 Analysis of Endpoints

We will analyse summary statistics for each allocation group, including means and standard deviations for normally distributed data and medians and interquartile ranges for non-normally distributed data.

Student's t test will be used to analyse the differences between the two groups (L-TME vs. R-TME). The paired t test will be used to compare postoperative urogenital, bowel and sexual functions in both groups to the preoperative functions. Fisher's exact test will be used for categorical data (e.g., age, sex, tumour location, T and N stage, and radiation therapy). A P-value of 0.05 will be considered statistically significant.

The analysis of the differences between groups of blood cell counts or number of lymphocyte subsets, and clinic pathological variables will be performed using Chi-square tests, Kruskal–Wallis tests, and analysis of variance tests. A P-value of 0.05 will be considered statistically significant.

Analysis of the QLQ-C30 and QLQ-CR29 questionnaires will be performed in accordance with the EORTC guidelines. Time to definitive deterioration in quality of life, with the use of a 10-point minimal clinically important difference, will be analyzed with the use of the Kaplan–Meier method and the log-rank test. Descriptions (by visit) and graphs will be presented.

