This study is looking to recruit a group of 80 patients with rectal cancer who are referred to the surgical department at Queen Alexandra Hospital for a surgical resection. We will compare the standard laparoscopic operation (Total Mesorectal Excision (TME) surgery) with robotic TME surgery. To compare the surgical stress response, we will take blood samples before the surgery and on day 1, 3 and 5 after the surgery. If all goes well day 5 is usually the day a patient is discharged home after this kind of surgery. To compare the functional outcomes, we will ask the patients to complete several questionnaires on urological function, sexual function, bowel function and general quality of life at several moments: before the surgery and after 3, 6 and 12 months. The research team will also gather further information about the recovery and cancer treatment by reviewing the patient's hospital notes for 1 year. This study will not affect the surgical after care of patients in both groups. After completing this study, we will

have better insight into which operation is better at causing the least harm to the surrounding structures when removing a rectal tumour.

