7. STUDY DESIGN

7.1 Summary of Study Design

A prospective, single centre, observational study with qualitative assessment of sexual, urological, bowel function and stress response in patients with rectal cancer comparing robotic surgery with laparoscopic surgery.

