8.3 Eligibility Criteria

Patient Inclusion Criteria

- Age 18 years or above.
- Diagnosed with rectal cancer, up to 15cm from the anal verge.
- Local MDT recommends rectal cancer surgery (i.e. (high) anterior resection, partial TME, complete TME)
- Patient assessed as fit for surgery (ASA I-III).
- Patient willing and able to give informed consent for participation in the study.
- Elective surgery.

Patient Exclusion Criteria

- Patient planned for Abdominoperineal Excision of Rectum (APER) or Hartmann's procedure
- Patients with confirmed or suspected metastatic disease.
- Pregnant or breastfeeding patients.
- Inflammatory bowel disease (IBD).
- Other known auto-immune disease which might influence the immune response (such as advanced liver disease, human immunodeficiency virus infection, Hepatitis B or C virus).
- Use of anti-inflammatory medication (i.e. corticosteroids, anti-inflammatory drugs, immune modulating drugs, chronic use of antibiotics (the use of NSAIDS and steroid asthma inhalers will not be considered an exclusion criteria).
- High pre-operative C-reactive protein (CRP) levels (>20).

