9. SAMPLING

In our retrospective study we demonstrated IPSS and IIEF score differences of more than 5.0 points between the 2 groups (see preliminary data). Assuming a 3.75 IPSS score and 4.4 IIEF score difference and a 0.05 (two-sided) significance level, 35 patients will be required in each group to provide 80% power.

We also carried out simulated cumulative scores from the study-specific CRF based on the Likert-scale for independent validation of our initial analysis. Considering 80% power and a 0.05 (two-sided) significance level, a minimum of 36 patients were needed in each arm to demonstrate a minimum difference in the cumulative score of 1 between the groups. This sample size calculation was carried out using the "stats" module in R (ver. 3.4.2) using a two-sided independent means test.

We have considered a maximum of 10% loss to follow-up for the long-term functional outcomes in our population during sample size calculations and will thus seek to recruit a minimum of 80 patients into our study.

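### Section 13.2 compares the two approaches with an unadjusted t test under a TME label, although eligibility also admits high anterior resection and approach is not randomised

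*Protocol*

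**What the plan says.** Eligibility (Protocol 8.3) covers tumours over the full height of the rectum, "Diagnosed with rectal cancer, up to 15cm from the anal verge", and three kinds of operation: "Local MDT recommends rectal cancer surgery (i.e. (high) anterior resection, partial TME, complete TME". High anterior resection is therefore listed apart from partial and complete TME.

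Two places name the comparison as TME against TME. The lay summary in section 5 says "We will compare the standard laparoscopic operation (Total Mesorectal Excision (TME) surgery) with robotic TME surgery". Section 13.2, which specifies the between-group test, says "Student's t test will be used to analyse the differences between the two groups (L-TME vs. R-TME".

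Other places compare by approach only. Section 7.1 describes "stress response in patients with rectal cancer comparing robotic surgery with laparoscopic surgery", and 6.1 and 6.3 are worded in the same way. Section 13.1 sets the analysis population by treatment completed and protocol deviations ("patients who completed the treatment as was originally allocated will be included in the analysis, as well as eligible subjects with no minor or major" deviations). It removes nobody for the type of resection.

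Section 8.1 states that patients are not randomised. Section 11.1 says the modality offered depends on which surgeon and theatre are available. Section 13.2 names no adjustment for the functional scores. Fisher's exact test is planned for tumour location and stage, which describes an imbalance but does not correct for it.

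**The concern.** There are two questions: which patients enter the functional comparison, and whether that comparison is fair.

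On the first, the labels in the lay summary and 13.2 do not match 8.3. A literal analyst would drop high anterior resections from both groups. Another would keep them and report the result as a TME result. If the choice is left open, it could be made after the data are seen.

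On the second, the protocol itself treats the type of resection as relevant to outcome. Section 4 says preserving function is harder for mid to very low tumours, because of the narrow pelvis and nearby structures, and links nerve damage to urological, sexual and bowel dysfunction. Section 5 explains the similar laparoscopic and robotic results of an earlier stress-response study by case mix, since all robotic tumours there were rectal. The same mechanism can act here. If one surgeon or theatre list takes more high resections, and these patients have different functional scores whatever the approach, the unadjusted t test attributes that difference to the approach.

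**Working it through.** **Inputs.** From section 9, the planning assumptions: "Assuming a 3.75 IPSS score and 4.4 IIEF score difference and a 0.05 (two-sided) significance level". The size derived from them is 35 per group at 80% power. Section 9 also gives a second calculation of 36 per arm for a cumulative-score difference of 1; 10% loss; 80 recruited. No standard deviation is given. Nor are the share of high anterior resections, or the types of resection to which the 3.75 and 4.4 points refer.

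**Step 1: the plan's own figure.** 2 × 36 = 72, and 72 / 0.9 = 80, so the total reproduces. Conversely 80 × 0.9 = 72, or 36 evaluable per arm. The 35 per group cannot be reproduced without a standard deviation, so it is solved backwards.

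**Step 2: implied effect size.** For a two-sample t test (two-sided 0.05, equal groups), power is the chance that a noncentral t variable with 2n − 2 degrees of freedom and noncentrality d√(n/2) exceeds the critical value.
- 35 per group at 80% gives d = 0.679, hence implied standard deviations of 3.75 / 0.679 ≈ 5.5 (IPSS) and 4.4 / 0.679 ≈ 6.5 (IIEF).
- 36 per arm at 80% gives d = 0.670.

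**Step 3: literal TME-only reading.** Assume a share s of high anterior resections, equal in both arms. Then n = 36(1 − s), with d unchanged.

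| s (assumed) | n per arm | Power, d = 0.679 | Power, d = 0.670 |
|---|---|---|---|
| 0 | 36 | 81.1% | 80.0% |
| 2.8% (one per arm) | 35 | 80.0% | 78.9% |
| 10% | 32.4 | 76.8% | 75.6% |
| 20% | 28.8 | 71.7% | 70.4% |
| 30% | 25.2 | 65.7% | 64.4% |
| 40% | 21.6 | 58.7% | 57.5% |

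The reserve is about one patient per arm for IPSS/IIEF and none for the cumulative score.

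**Step 4: pooled reading.** Here n stays at 36.
- If 3.75/4.4 is the average difference over all eligible patients, power is 81.1% at every s.
- If it holds in TME patients alone and high resections show no difference at all, the effect becomes d(1 − s). Power is then 61–62%, 50–51% or 39–40% at s = 20%, 30% or 40%. This is a worst case.

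**Step 5: bias from unequal shares.** Let the share of high resections be p_R in the robotic arm and p_L in the laparoscopic arm. Let these patients' mean score differ from that of TME patients by Δ, whatever the approach. With no true effect of approach, the unadjusted comparison estimates (p_R − p_L) × Δ. Neither quantity is in the protocol. For illustration, assume Δ equals the planned difference:

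| Imbalance (assumed) | IPSS, Δ = 3.75 | IIEF, Δ = 4.4 |
|---|---|---|
| 10 points | 0.10 × 3.75 = 0.375 | 0.10 × 4.4 = 0.44 |
| 20 points | 0.20 × 3.75 = 0.75 | 0.20 × 4.4 = 0.88 |
| 30 points | 0.30 × 3.75 = 1.125 | 0.30 × 4.4 = 1.32 |

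Under that assumption the bias is 10%, 20% or 30% of the difference the study is planned to detect, and it can run in either direction.

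These figures take 36 evaluable patients per arm, as the plan does. That IPSS and IIEF apply to men only is a separate matter and is not counted here.

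**The case against.** The strongest reply is that this is only a label. The study has two groups, set by approach. The title uses TME as an umbrella term, 6.1, 6.3 and 7.1 compare by approach, and 13.1 removes no type of resection. A lay summary does not define an analysis. This stands: the wording is unclear rather than contradictory, and nothing instructs an analyst to drop eligible patients. Relabelling alone would be clerical.

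A reader might infer that the 80% power is lost on either reading. The documents do not support that. The pooled loss in step 4 needs an assumed share, no effect of approach in high resections, and planned differences that hold in TME patients alone. Section 9 states none of these, and section 5 describes the retrospective study behind the figures simply as rectal cancer surgery. Section 4 describes a gradient of difficulty, not the absence of an effect in higher tumours. The planned differences are also smaller than the more than 5.0 points seen before. At 5.0 points with the same implied standard deviations, a TME-only analysis would keep 80% power with about 21 (IPSS) or 28 (IIEF) per arm.

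A reader might also infer that TME groups could not be formed from the data. That goes too far. The surgical outcomes in 7.2 are an open list, patient records are reviewed (10.2), and the content of the CRF is not shown. One can say only that type of resection is not a named variable.

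Finally, stratification may be called detail for a statistical analysis plan. But 13.2 itself fixes a plain t test for a non-randomised comparison, so the choice is the protocol's own.

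**Conclusion.** The point holds as a low-cost improvement to the analysis, not as a failure of the sample size. The labels in the lay summary and 13.2 do not match eligibility, and the protocol should say which resections enter the functional comparison.

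The substantive weakness is the unadjusted test. In a non-randomised study whose own rationale says functional risk varies with the depth of dissection, an unequal share of high resections biases the estimate directly. The size of that bias cannot be fixed from the protocol, and step 5 is only an illustration.

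The loss of power is conditional. It applies at the planned differences if TME is read literally: below 80% once more than about one patient per arm is left out, and about 70–72%, 64–66% or 58–59% at assumed shares of 20%, 30% or 40%. On the more natural pooled reading, power stays near 81% unless the planned differences are taken to hold in TME patients alone.

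**What to change.** - In 13.2, define the groups as laparoscopic versus robotic resection in all eligible patients, and use the same label in the lay summary.
- Replace the unadjusted t test for the functional scores with a comparison stratified by, or adjusted for, type of resection (high anterior resection, partial TME, complete TME). The MDT-recommended operation is preferable as the variable, because the operation actually performed may itself depend on the approach.
- Record that variable in one CRF field.
- Base any statement about TME surgery on the partial-or-complete-TME subset, specified in advance and reported as supportive.
- In section 9, state the population to which the 3.75 and 4.4 points refer and the standard deviations used.

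The cost is one extra field, a few reworded sentences and a few degrees of freedom. The TME-only estimate will be less precise than the full-sample one, which is why it should be supportive. No treatment or visit changes.
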